The objectives of this study were to evaluate the inhibitory effect on plaque and the tooth discoloration associated with agents used in the chemical plaque control of oil pulling in comparison with chlorhexidine-containing mouthwash and water in a four-day plaque regrowth model.

Study Design

At the beginning of a two-week preparation period, plaque, calculus and dental stains will be thoroughly removed, both hand and by ultrasonic scaling and polishing, and oral hygiene instruction will be provided for self-administered plaque control (Fig. 1). At the end of the preparation period, all participants are expected to have clinically healthy gingivae. The participants will randomly divided into five groups, and the coded allocated product will be provided. The instructions for use of the allocated products will be given to the individuals with a printed program by a dentist who will not involved in the study. On day 1 of the study, after the plaque has been stained with a plaque disclosure tablet (Curaprox, Kriens, Switzerland), all participants will undergo scaling and polishing to remove plaque and tooth staining, and teeth will be redisclose with a tablet to ensure that all the participants will be provided with a zero plaque score at the start of the trial. Then, the tooth color will be determined with a digital spectrophotometer (VITA Easyshade® V; VITA Zahnfabrik, Bad Säckingen, Germany). Afterwards, individuals will asked to avoid all types of dental cleaning and to follow the study protocol. The participants will be instructed to avoid other mouthwashes, chewing gum, or the use of toothpaste during the four-day period. They will be instructed to control the application time with a timer and will be reminded twice a day to use the allocated products for a four-day period by the dentist who assigned the product. At the end of the fourth day, tooth color will be redetermined with the VITA Easyshade® V. The teeth will then disclosed with a Curaprox® plaque staining tablet, and plaque scores will record using the Quigley-Hein and Turesky plaque index (Q-H) (Quigley & Hein, 1962; Turesky et al., 1970). Finally, the gingival index (GI) will be recorded. All clinical examinations will be performed by a blinded observer. After the clinical parameters will be recorded, the teeth will polish to remove all plaque and any tooth staining.

Clinical Examinations

The Quigley-Hein and Turesky plaque indexes (Quigley & Hein, 1962; Turesky et al., 1970) will be used to measure dental plaque formation and the degree of deposition, and gingival index (Loe & Silness, 1963) to evaluate gingival inflammation. To assess tooth color change, tooth color determination will be performed at the beginning and end of the study with the VITA Easyshade® V digital spectrophotometer and will record as a CIE L* a* b* value. Measurements will make under D65 standard lighting conditions corresponding to daylight, and the device will be calibrated before each measurement. Color measurements will make from the middle third of each participant's right maxillary central incisor tooth. The color of the tooth will be determined three times, and the average CIE L* a* b* value will be obtained.

The color difference (ΔE) values of the teeth at the beginning (L_0 , a_0 , b_0) and the end (L^* , a^* , b^*) of the study will be calculated by using the following CIELAB color difference formula:

$$\Delta E = [(\Delta L)^2 + (\Delta a)^2 + (\Delta b)^2]^{1/2},$$

($\Delta L = L^* - L_0$, $\Delta a = a^* - a_0$ ve $\Delta b = b^* - b_0$)

The L^* , a^* and b^* values represent the color values measured at the end of four days, while the L_0 , a_0 and b_0 values represent the color values measured at the beginning of the study.

Statistical Analysis

The data obtained as a result of the measurements made by the participants after using different products will be analyzed using a statistical software program (IBM SPSS Statistics, v23.0®; IBM Corp., Chicago, IL, USA). Because the group number is more than three, (CHX, DW, coconut oil, turmeric oil, black cumin oil) the parametric method (ANOVA) will be used in the analysis of normally distributed data. Also, homogeneity of variance, another assumption of the ANOVA test, will also be tested during the analysis. For the multiple comparison tests, the Tukey method will be used in homogeneous groups, and the Games-Howell method will be used in non-homogeneous groups, depending on the number of samples in the groups (Tabachnick et al., 2007). Analyses will be performed at a 95% reliance interval ($\alpha=0.05$).

Figure 1 Flow chart of the study.

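### Tooth discoloration is an objective, but the only color-change outcome defined is the unsigned ΔE, which cannot by itself tell staining from lightening

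*Combined protocol and SAP*

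**What the plan says.** The opening objectives include "the tooth discoloration associated with agents used in the chemical plaque control of oil pulling". The agents are to be judged against two comparators, that is, "in comparison with chlorhexidine-containing mouthwash and water in a four-day plaque regrowth model".

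Clinical Examinations records tooth color as CIE L*, a* and b* at the beginning and end of the study. Three readings are taken on one incisor, "and the average CIE L* a* b* value will be obtained". The section then defines one measure of change, "The color difference (ΔE) values of the teeth at the beginning" and the end: ΔE = [(ΔL)² + (Δa)² + (Δb)²]^½. The signed differences ΔL, Δa and Δb are written out, but only as terms of that formula.

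Statistical Analysis lists no outcome by name: "The data obtained as a result of the measurements made by the participants after using different products will be analyzed". It plans ANOVA across five groups, then Tukey or Games-Howell comparisons, at α = 0.05. It mentions neither a signed color comparison nor a baseline covariate.

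Study Design fixes the order of dye and color reading. On day 1, after scaling and polishing, "teeth will be redisclose with a tablet to ensure that all the participants will be provided with a zero plaque score". Only after that step does the text turn to the baseline reading: "at the start of the trial. Then, the tooth color will be determined with a digital spectrophotometer". On day 4 the order is reversed: "tooth color will be redetermined with the VITA Easyshade® V. The teeth will then disclosed with a Curaprox® plaque staining tablet".

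**The concern.** Discoloration has a direction and ΔE does not. If an oil arm has a higher mean ΔE than water, its teeth changed color more, but they may have become darker, lighter, redder or less yellow. The objective asks about staining, and the values that would show it (L*, a* and b* at both visits) have no planned comparison. Direction could be examined afterwards, but three coordinates and ten pairs of arms leave room for selective reading.

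A second feature of the design adds to this. Baseline color is read after a disclosing tablet, end color before one. The plan does not say that dye remains on the teeth at baseline. If some did, every arm would carry the same artificial change. That change cancels when signed changes are compared between arms, but not in ΔE.

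**Working it through.** The plan gives no sample size, SD, correlation or expected color change, so it has no figure to reproduce. Step 1 uses only the plan's formula. The later steps illustrate size under stated assumptions.

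**1. Sign.** Put two opposite changes (ΔL, Δa, Δb) into the formula:
- Darker and yellower (-3, 0.5, 2): √(9 + 0.25 + 4) = √13.25 = 3.64
- Lighter and less yellow (3, -0.5, -2): √(9 + 0.25 + 4) = 3.64

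**2. Opposite arms.** Assume mean changes of (-2, 0.3, 1.5) in one arm and the mirror image in another, SD 0.5 to 1.5 per coordinate, n = 10 to 30 per arm, and two-sample t-tests at 0.05 (4,000 simulated trials per setting).
- Darkening against lightening is significant on ΔE in 4.8% to 5.6% of trials, which is the error rate, and on signed ΔL in at least 99.9%.
- Lightening against no change is significant on ΔE in 46% to 100% of trials. A higher ΔE can therefore arise with no staining at all.

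**3. Power in the planned five-arm comparison.** Assume SD of change 1 per coordinate, independent coordinates, one arm shifted and compared with water, pooled-variance Tukey over five arms, and n = 15 per arm (range 10 to 30). Signed coordinates use Holm over the three. Tukey critical t at n = 15 is 3.21, 3.06 and 2.80 at levels 0.05/3, 0.025 and 0.05 (20,000 simulated trials per case).

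Mean ΔE is 1.60 with no shift. It is 2.50 for +2 SD in b*, -2 SD in b*, +2 SD in a*, or 1.155 SD in all three (1.155 × √3 = 2.00).

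| True shift | Power on ΔE | Power on signed coordinates |
|---|---|---|
| 1 SD in b*, n = 15 | 0.05 | 0.33 |
| 1 SD in b*, n = 10 | 0.03 | 0.17 |
| 1 SD in b*, n = 30 | 0.10 | 0.76 |
| 1 SD in L* and b* | 0.20 | 0.55 (at least one) |
| 1 SD in all three | 0.46 | 0.37 each; 0.70 at least one |
| 1.155 SD in all three | 0.71 | 0.56 each; 0.87 at least one |
| 2 SD in a* only | 0.71 | 0.99 |
| 3 SD in b* only | 1.00 | 1.00 |

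For 2 SD in a* only, testing just L* and b* would give 0.006, so no coordinate should be left out.

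**4. Baseline adjustment.** With the SD of change held at 1 and baseline-end correlation ρ, the ANCOVA residual SD is √((1 + ρ)/2): 0.866, 0.922 and 0.975 for ρ = 0.5, 0.7 and 0.9. Power for 1 SD in one coordinate at n = 15, after Holm, is then 0.48, 0.41 and 0.35, against 0.33 without adjustment.

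**5. Common baseline offset (assumed).** Let the product add 2 SD in a* and residual dye add an opposite change to every arm.
- Offset 1 SD: the net change is 2 - 1 = +1 on product and -1 on water. Mean ΔE is 1.85 in both arms and power is 0.007.
- Offset 2 SD: the net change is 0 on product and -2 on water. Mean ΔE is 1.60 and 2.49, and the test is significant in the wrong direction with probability 0.55.
- Offset 0.5 SD: power 0.17. No offset: 0.71. Offset of 1 SD in the same direction as the product: 0.98.

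Power on signed a* stays at 0.99 with every opposing offset.

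**6. Multiplicity.** Family-wise error over all ten pairs at n = 15 is 0.048 for ΔE alone, 0.049 for Holm over the three coordinates alone, and 0.094 if both are tested at 0.05.

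**The case against.** The strongest reply is that a signed analysis is left unspecified, not ruled out. Statistical Analysis names no outcome of any kind, and the coordinates are recorded. That is true, and it is why the point is limited to what ΔE can show by itself. But ΔE is the only change measure the plan defines, and nothing commits the trial to a directional comparison.

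Teeth are scaled and polished before the baseline reading, and participants then avoid all cleaning for four days. Staining is therefore the more likely direction, and the mirror-image arms in step 2 are a constructed contrast. This lowers the practical risk of mistaking lightening for staining, but it gives ΔE no sign.

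The dye argument is conditional. Its worst figures need an offset of 1 to 2 SD opposite to the product effect, equal on average in all arms. It should be read as a further reason to plan signed comparisons, not as a demonstrated bias.

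The power figures are also mixed, and they use pooled variance. Games-Howell, which the plan reserves for unequal variances, lowers ΔE power at n = 15 from 0.71 to 0.59 for 2 SD in a*, and from 0.46 to about 0.35 for 1 SD in all three. The second decimal should not be relied on.

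Finally, reporting the coordinate changes by arm with confidence intervals would close most of the gap. Baseline adjustment and Holm are refinements, and the gain from adjustment depends on a correlation that the plan does not give.

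**Conclusion.** The concern holds. As defined, a between-arm difference in ΔE shows that color changed more in one arm, not that teeth stained more, and the objective is about discoloration. This conclusion rests on the formula alone.

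The fault is limited. ΔE is a valid measure of total color change, and its use does not inflate type I error between arms. The power advantage of signed coordinates is large only for small shifts confined to one or two coordinates; for spread shifts ΔE beats any single coordinate, and for large shifts both detect the difference. All power figures rest on an assumed n, SD, independence of coordinates and effect size. The dye figures rest further on an assumed residue that the plan does not report.

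**What to change.** - Keep ΔE as the color outcome tested between arms at 0.05 with the planned Tukey or Games-Howell procedure.
- Add, as pre-specified secondary analyses, between-arm comparisons of end-of-study L*, a* and b*, including each arm against water. Use ANCOVA with the same coordinate's baseline as covariate, and report adjusted differences with 95% confidence intervals.
- Treat the three coordinates alike, with Holm over the three if they are tested.
- State that these results support the reading of ΔE and are not additional claims of success, since testing both at 0.05 would raise family-wise error to about 0.09.
- Interpret signed results as differences between arms, mainly against water, and not as change within an arm, because the two color readings differ in dye exposure.

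The cost is analysis-plan wording and three extra secondary results; no new data, visits or participants are needed. Holm reduces power per coordinate: at 1 SD and n = 15 the noncentrality is 1/√(2/15) = 2.74 against a critical t of 2.80, giving 0.48 without Holm and 0.33 with it. Baseline adjustment recovers a useful part of this only if the baseline-end correlation is moderate.
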